ADD NEW PROTOCOL AT THE SAME PATIENTS

INTRODUCTION

The term low back pain is characterized by pain in the lumbar spine region, a condition that affects individuals of both sexes and reduces their ability to perform activities in their daily lives, which results in a substantial economic cost to society ¹. Notably, approximately 70% of the population of Brazil may have an episode of low back pain during their lifetime ^{2,3}.

The etiology regarding the development of low back pain is still unclear due to the innumerable factors that may lead to its onset, some of which may be related to repetitive work, pulling and pushing, falls, poor posture, squatting, heavy lifting, muscle imbalance, and compressive syndromes, among others. Chronic pain is among the main causes of absenteeism at work, medical leave, sick leave, workers' compensation, and low productivity at work ^{1,4–6}.

It is important to emphasize that limited mobility of the lumbar spine due to pain can often be associated with this condition ⁴. Another extremely relevant point with regard to spinal nerve injuries, particularly in the lumbar region, is that they are often caused by compressive syndromes such as discal hernias. Such compressions often result in neuropathic pain, which is characterized by spontaneous burning pain, followed by allodynia and hyperalgesia, which can be observed in the nerve pathways of the in the lower limbs ⁵.

In addition to pharmacological and surgical treatments, there are noninvasive or nonpharmacological treatments such as physiotherapy. Physiotherapy treatments, which have countless approaches, facilitate a decrease in signs and symptoms, such as reduced pain and muscle tension and increased lumbar and hip range of motion, in individuals with chronic low back pain ⁷. One of the available treatments is neural mobilization (NM), which is characterized by a set of techniques that aim to impose greater tension on the nervous system through certain postures; slow and rhythmic movements are applied to the peripheral nerves and spinal cord, improving conduction of the nerve impulse ⁸.

Studies have demonstrated the beneficial effects of NM, including improved joint pain in patients with rheumatoid arthritis ⁹ and improved cervicobrachial pain ¹⁰. Neural mobilization has demonstrated an excellent prognosis in patients with this type of pain, in addition to presenting other advantages such as low operational cost, easy application and no adverse effects.

Results from the previous studies described above show the beneficial effects of NM treatment. There is a lack of clinical trials regarding the use of NM for different types of pain.

The aim of this study was to compare pain intensity and functional capacity before and after treatment with NM in volunteers with chronic low back pain.

The research questions were as follows:

- 1. What are the effects of the neural mobilization technique on individuals with chronic low back pain?
- 2. Is neural mobilization effective?

METHOD

Participants, therapists, center

The participants were recruited for evaluation by establishing the inclusion and exclusion criteria of the study. Individuals of both sexes who met the following criteria were included in the study: chronic low back pain, radiating or not to one of the lower limbs; age 18 years or older; score ≥ 4 on the visual analog scale (VAS).

We excluded individuals with acute low back pain; spondylolisthesis or fibromyalgia; previous spinal surgery; any sequelae that caused limitations in the range of motion of the lower limb or joint deformity; metal plates, screws, neurological disorders who present caution for neural mobilization; cancer; cognitive disturbances or apparent limitations; any type of pain in other regions that is not characteristic of low back pain; advanced diabetes mellitus; under physiotherapeutic treatment for the same reason; decompensated cardiovascular diseases; significant changes in sensitivity; edema in the lower limbs; and pregnant women.

After eligibility was confirmed, all the procedures to be performed during the study were elucidated, and the subjects signed the Free and Informed Consent Terms, according to Resolution 466/12 of the National Health Council - Brazil, confirming their participation in the research.

Sixteen volunteers, 8 women and 8 men, with a mean age of $30,45 \pm 10,32$ years, participated in this study. After being selected, the volunteers were allocated to Group NM, consisting of individuals with low back pain, and were treated with the technique.

After fulfilling the eligibility criteria, a clinical evaluation and assessments of pain intensity, spinal mobility, peripheral sensitivity and hip goniometry were carried out, and a quality of life questionnaire was administered (details below).

To preserve the accuracy of the intervention effectiveness, participants who missed more than two sessions were excluded from the study. All subjects were assessed by a blinded evaluator. Both participants and evaluators were encouraged not to discuss the intervention.

Intervention

The Neural Mobilization technique was performed by the same physiotherapist from the first to the last session on alternate days. Treatment with the technique consists of applying a total of 10 interventions in each patient, with a total duration of 10 minutes, divided into four series of 2 minutes each, with a 30 second interval between each series, according to the protocol proposed in 2012 by Santos et al.¹¹.

The technique was applied with the participant seated in a suitable chair, with a flexed hip (90) and extended knees (Figure 1). Next, the physiotherapist applied the technique only to the lower limb in which the individual presented with some impairment due to low back pain, observed in the previous physical examination; in case of absence of pain radiation to any of the limbs, the technique was applied only to the right lower limb according to Santos et al. 2012¹¹.

During the period from July 2016 until September 2017, we screened 60 subjects for eligibility; of those, only 16 individuals completed the entire study protocol according

to the inclusion and exclusion criteria. Table 1 shows a flowchart of the study design that explains all the procedures implemented with the volunteers in all groups.

Calculation of the sample

The sample size was calculated based on the visual analog scale for pain, which was considered the primary end point. To this end, the variance reported in the study by Murphy et al., 2006, whose objective was to evaluate neural mobilization as a technique for treatment. Considering the mean and standard deviation of the pre-intervention and post-intervention of this study, with an alpha value (α) of 0.05 and 90%, it was determined that 20 subjects were required for the experimental group ¹².

Outcome measures

First, all personal data from each subject were obtained, including age, occupation and education. After this first step, the participants submitted to two evaluations, one prior to and one at the end of the therapeutic program. Both evaluations were to assess pain intensity and mobility of the lumbar spine and to measure cytokines.

Visual Analog Scale (VAS):

A visual analog scale was used for the assessment of pain intensity; it consists of a line ranging from 0 to 10, where zero represents the absence of pain and ten represents the worst pain. After instruction in how to complete the scale, the volunteer was asked to mark a point on the line that indicated the intensity of the pain that he or she was feeling at the moment of evaluation 13 .

Mobility of the lumbar spine:

Two tests were used to evaluate the mobility of the lumbar spine: the 3rd finger to the ground and goniometry.

The test of the 3rd finger to the ground distance consists of an active test in which the individual is placed in an orthostatic position, with the feet separated in line with the hips, keeping the knee extended and heel touching the ground. Then, the participant is asked to perform trunk flexion with the arms extended and to try to bring his hand

closer to the ground. Then, using a tape measure, the distance between the tip of the 3^{rd} finger and the ground is measured, and the value in centimeters is considered the mobility of the volunteer's lumbar spine ^{1,14}.

Goniometry refers to the measurement of individuals' joint angles; it was applied before the first session and after the last session of neural mobilization. To minimize measurement error, the physiotherapist in charge underwent training. Goniometric measurements of the hip joint of the participants in this study were used for both thigh flexion; the amplitude varies between 0 - $131^{\circ} \pm 6.4^{\circ}$, and the articular range varies from 0 to $13^{\circ} \pm 5.4^{\circ}$; measurements may vary from individual to individual more or less within these established values ¹⁵.

Evaluation of Cytokines:

Blood was collected from each group to evaluate the possible impact of the technique on pro- and anti-inflammatory cytokines. Two collections were performed: the initial measurement (I) and the final measurement after the last session (F) of treatment. To evaluate the cytokine concentration, the blood serum of the individuals was used for these analyses.

For specific IL-1 β , IL-4, IL-6, and FTN- α cytokines, specific reagents contained in the Milliplex[®]TM Map kit (Millipore Corporation, Darmstadt-Germany) were assessed by Multiplex (Enzime-Linked ImmunoSorbent Assay) according to the protocol specified by the manufacturer.

Data analysis

The statistical analysis consisted of ANOVA with repeated measures for the time factor, which was performed to test between-group differences (followed by the Tukey-Kramer post hoc test), and a paired *t*-test was performed to test within-group differences. The results were considered statistically significant if $p \le 0.05$, using the standard error of the mean \pm SEM ¹⁸.

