Thirty-five individuals volunteers participated in this study, with a mean age of 49.64 years, were 21 women and 14 men. After being selected, the volunteers were allocated to three groups: Neural Mobilization Group (MOB), consisting of individuals with low back pain and treated with the technique, with a total of 18 participants; Neural Mobilization + Medication Group (MOB + MED), constituted by individuals with low back pain, who underwent the mobilization technique associated with medication, a total of 12 participants; and the control group (CONTROL) constituted by healthy individuals without any kind of injury or pain complaint who received the application of the neural mobilization technique, with a total number of 5 participants.

After fulfilling the eligibility criteria, a clinical evaluation and assessments of pain and mobility were carried out, and a quality of life questionnaire was applied (details below).

In order to preserve the accuracy of the intervention effectiveness, participants who missed more than two sessions were excluded from the study. All subjects were assessed by a blinded evaluator. Both participants and evaluator were encouraged not to discuss the received intervention.

First, all personal data from each subject were obtained. Age, body mass, height, profession, school education. After this first step, the participants were submitted to two evaluations, prior to and at the end of the therapeutic program. Both to assess the pain

intensity and to assess the mobility of the lumbar spine, as well as the application of a quality of life questionnaire. A follow up was done thirty days after the end of the treatment to verify the effect of the protocol after the patients return to the normal daily life activity. A characterization and physical examination card were used for a better analysis of the volunteers. The subjects in all three groups were submitted to the same evaluation protocol.

A visual analogue scale (VAS) was used for the assessment of pain intensity, which consists of a line ranging from 0 to 10, where zero characterizes absence of pain and ten, worst pain. After clarifying how to complete the scale, the volunteer was asked to mark a point on the line that indicated the intensity of pain that he or she was feeling at moment of the evaluation [9].

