The Neural Mobilization technique was performed by the same physiotherapist, from the first to the last session, on interleaved days. The protocol of the technique consists in applying a total number of 10 interventions in each patient, with a total duration of 10 minutes, divided into four series of 2 minutes with a 30-second interval between each series according to the protocol proposed in 2012 by Santos et al [15].

The technique was applied with the participant seated in a suitable chair, with a flexed hip (90) and extended knees (figure 1). Next, the physiotherapist applies the technique only to the lower limb in which the individual presents some impairment due to low back pain, observed in the previous physical examination, or in case of absence of irradiation for any of the limbs, the technique was applied only to the right lower limb according to Santos et al 2012 [15].

In the period from July 2016 until September 2017, we screened 60 subjects for eligibility but only 35 individuals had finished all the study protocol according to the includes and exclude criteria. Next, in figure 2 we have a flowchart about the study design, that explain all the procedures realized with the volunteers in all groups.

The statistical analysis was the ANOVA test with repeated measures for the time factor were performed to test between-group differences (followed by the Tukey-Kramer post hoc test), and a paired t test was performed to test within-group differences. The level of significance for the statistical analysis was 5% ($p \le 0.05$), using the standard error as mean \pm SEM [16].

RESULTS:

A total of 35 patients concluded the study and were analyzed. Characteristics of participants included in each group were presented in Table 1 and were homogenous for age at baseline. After the application of the Neural Mobilization technique, the patients were reassessed and the data obtained in both, the initial and final evaluation were submitted to statistical analysis.

Visual Analogue Scale:

Our results demonstrated an improvement in pain in patients treated with neural mobilization. There was a mean reduction in the VAS scale from average 8.47 to 4.05, which was statistically significant in group MOB (Figure 3).

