The decrease of pain sensitivity started at the 4th session for patients treated with neural mobilization only (MOB) and from the 5th treatment session for the patients using medicament plus therapeutic treatment group (MOB + MED). The improvements remained until the end of the treatment (Figure 3).

EVA was 1.5 for MOB group and 2.6 for MOB+MED thirty days after the end of the sessions. Control group (CONTROL), composed of individuals without any kind of pain or injury and who were treated with the neural mobilization technique, it was noted pain intensity on the VAS scale remained at zero until the follow up evaluation (Figure 3).

It should be mentioned that it was not possible to observe a statistically significant difference between the MOB and MOB + MED groups, which suggests that the Neural Mobilization technique alone can improve the pain of these individuals, and it could be considered an adjuvant therapy to the drug treatment of patients (Figure 3).

Roland-Morris Disability Questionnaire (RMDQ):

By adding the yes answers and reaching a value equal to or lower than 10 points, it shows that the person with low back pain presents without some kind of disability, that is, despite the pain, there is no impeding the accomplishment of their daily life tasks. However, if the total varies between 11 and 14 yes / indicated alternatives, it indicates a mild or moderate inability of this individual to perform their daily activities. When the positive responses are equal to or greater than 15, it indicates that this individual has a severe disability [12].

In the MOB group, 17 individuals were evaluated. In the initial measurement, we observed that 15 individuals presented in the normal parameter, not showing any kind of incapacity in performing daily life activities. Two individuals from the same group, presented, in the initial measurement, a severe incapacity to perform the activities of daily living. At the end of the treatment, this questionnaire was reapplied, and 16 of the subjects presented normal parameters, and one of the individuals with severe disability returned to normal levels; the other individual who also presented a severe level of disability, partially reversed their condition, going to mild/moderate disability when performing activities of daily living (Table 2).

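### Removing participants who missed more than two of the 10 sessions, with no analysis of all who started, restricts the pre-post results to the retained set, and the conclusions do not say so

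*Protocol*

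**What the plan says.** The rule appears in the same words in the Protocol (METHOD, Participants) and the Combined document (MATERIALS AND METHODS): "participants who missed more than two sessions were excluded from the study". Both give its purpose as protecting the accuracy with which effectiveness is measured. Both plan 10 sessions per patient.

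The analysis text (Protocol, Data analysis; Combined document, end of MATERIALS AND METHODS) names repeated-measures ANOVA with Tukey-Kramer comparisons and a paired t-test. Neither text defines an analysis set of all who started or a method for missing values.

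The counts in the running text are:

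- Protocol: "Sixteen volunteers, 8 women and 8 men" took part, and "we screened 60 subjects for eligibility; of those, only 16 individuals completed the entire study protocol".
- Combined document: "Thirty-five individuals volunteers participated in this study", "we screened 60 subjects for eligibility but only 35 individuals had finished all the study protocol", and "A total of 35 patients concluded the study and were analyzed".

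The Protocol reports no pain results. The Combined document does: "There was a mean reduction in the VAS scale from average 8.47 to 4.05, which was statistically significant in group MOB". Its DISCUSSION says that every individual improved significantly in pain, and its CONCLUSION calls the technique effective in people with chronic low back pain. Neither mentions attendance.

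**The concern.** Missing a third session can happen only after treatment has started, so the rule is not an eligibility criterion. It selects the analysed set on something that response may influence. Patients who feel no benefit may stop coming, and so may patients who recover early. The first kind of loss would make the average improvement look too large, the second too small.

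The stated aims concern patients with chronic low back pain who are given the technique. Under the rule, the pre-post change is that of the patients who were retained. The between-group comparisons use the same set. At stake are the size of the reported improvement and the population to which it applies.

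**Working it through.** **1. What the rule implies.** Ten sessions with at most two missed leaves a minimum of 10 - 2 = 8 attended. This is the floor set by the rule, not a known attendance. Both documents describe the analysed participants as having finished the whole protocol, so all of them may have had 10 sessions.

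**2. What the counts show.** Participating and finishing numbers are equal: 16 and 16 in the Protocol, 35 and 35 in the Combined document. Either nobody was excluded or only finishers were counted. The visible text cannot separate the two. The flowcharts, which are not shown, may do so.

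**3. The reported change.** In the MOB group the VAS fell by 8.47 - 4.05 = 4.42. With 18 patients, the summed fall is 18 × 4.42 = 79.56. The sentence gives no time point for 4.05. It is not the follow-up value, because "EVA was 1.5 for MOB group and 2.6 for MOB+MED thirty days after the end of the sessions" (reading EVA as the VAS). I take it as the final measure.

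**4. Illustration.** Let k be the number of MOB patients excluded under the rule. No positive k is documented; the values of k are assumptions. Let b be the excluded patients' mean baseline.

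- No change in the excluded: 79.56 / (18 + k), whatever b is.
- Full recovery to VAS 0: (79.56 + k × b) / (18 + k).

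With b = 8.47, the completers' baseline:

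| k | No change | Full recovery |
|---|---|---|
| 0 | 4.42 | 4.42 |
| 2 | 79.56 / 20 = 3.98 | (79.56 + 16.94) / 20 = 4.83 |
| 6 | 79.56 / 24 = 3.32 | (79.56 + 50.82) / 24 = 5.43 |

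The baseline of excluded patients is also unknown. The documents bound it by the entry score (at least 4) and the scale maximum (10). Over that range the full-recovery figure is:

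- k = 2: (79.56 + 8) / 20 = 4.38 to (79.56 + 20) / 20 = 4.98.
- k = 6: (79.56 + 24) / 24 = 4.32 to (79.56 + 60) / 24 = 5.82.

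Worsening in the excluded is not covered.

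**5. Shortfalls that are visible.** The Combined document allocates 18 to MOB and 12 to MOB + MED. The RMDQ results cover 17 and 11, so one is missing in each group. The ODI rows in Table 3 sum to 7 + 7 + 1 + 1 = 16 and 8 + 3 = 11 at the initial measure, and 14 + 1 + 1 = 16 and 7 + 2 + 2 = 11 at the final measure, so two and one are missing. No reason is given, and nothing ties these to the attendance rule. They do show that the 35 analysed do not contribute to every outcome.

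**The case against.** The strongest reply is that no loss has been shown. The equal counts are compatible with nobody having been excluded. Both documents tie the drop from 60 screened to the inclusion and exclusion criteria, and the flowcharts may hold the missing numbers. The rule is openly stated. A fall of at least 3.32 points remains in every scenario shown above. The controls are healthy, so adding starters would not show that the technique caused the fall. Replacing the analysis once results are known is itself post hoc.

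Much of this stands. It means that the point cannot be put as a demonstrated bias, and that a request for counts alone might already be met by the flowcharts. It does not remove the rule, which conditions on attendance after the start of treatment, or the absence of any all-starters analysis from analysis text that is visible. Disclosing the rule in the methods does not extend the result to those it removes.

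A reader might infer more than the documents support:

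- *That 60 - 16 = 44 or 60 - 35 = 25 people were lost under the rule.* Both gaps include screening failures. The Protocol's title line presents it as an added protocol in the same patients, and it gives the same 60 screened over the same dates. If there was one screened pool, the 44 may include people who finished the Combined study.
- *That the improvement is inflated.* The direction is unknown, and k may be zero.

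**Conclusion.** The concern holds in a limited form. Both documents remove low attenders after treatment has started and plan no analysis of all who started. The Combined document's pre-post results, and those planned in the Protocol, are restricted to participants with at most two missed sessions. The Combined document's discussion and conclusion omit that restriction.

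Whether this altered any number cannot be determined from the text. If nobody was excluded, the 4.42-point fall stands as reported. With two exclusions it would lie between 3.98 and 4.83. That range assumes k = 2, the completers' baseline, 4.05 as the final measure, and outcomes for the excluded between no change and full recovery. The existence of a pre-post fall in MOB is not threatened in the scenarios shown; its size and the patients it describes are. This should be corrected, with medium confidence because the number excluded is unknown.

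**What to change.** 1. In the analysis, replace the exclusion rule with an analysis of all pain patients who received at least one session, using every VAS value kept for them. Report the set with at most two missed sessions alongside it. Because results are already known, label the all-starters analysis as added post hoc. In the Combined document, session-level VAS values appear to exist (RESULTS and the Figure 3 legend), although the described evaluation schedule does not list them. The Protocol has only two evaluations.
2. Where no final VAS exists, give a two-directional sensitivity range: no change and full recovery.
3. Report the numbers started, excluded for attendance and analysed, separately for each outcome, and explain the RMDQ and ODI shortfalls. If nobody was excluded for attendance, say so: the two sets then coincide and no re-analysis is needed.
4. Until this is done, or the counts show no exclusions, limit the conclusions, including the statement that all individuals improved, to participants who missed no more than two of the 10 sessions.

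The cost is a set of counts and a limiting sentence, plus a re-analysis only if someone was excluded. The downside is a possibly smaller and noisier estimate. The recruitment period given ended in September 2017, so some values may be unobtainable.

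### The Protocol plans 20 subjects for the primary VAS endpoint, reports 16, and does not restate the power: about 82% if 20 gave 90% with no dropout allowance

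*Protocol*

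**What the plan says.** In the Protocol, the section on calculation of the sample takes VAS pain as the basis, "which was considered the primary end point". It cites an earlier study for the pre- and post-intervention mean and standard deviation, sets alpha at 0.05, adds 90% without saying of what, and concludes: "it was determined that 20 subjects were required for the experimental group".

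The participants section reports "Sixteen volunteers, 8 women and 8 men", all allocated to the single treated group. The Intervention section says "we screened 60 subjects for eligibility" and that "only 16 individuals completed the entire study protocol". The Method section also states that "participants who missed more than two sessions were excluded from the study".

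For the study design and procedures the Intervention section points to a chart: "Table 1 shows a flowchart of the study design". That chart is not in the text available for this review. The Combined protocol and SAP contains no sample-size calculation.

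**The concern.** The planned and achieved sizes stand close together in the Protocol, and nothing connects them. No sentence gives a revised target, a dropout allowance or the power at 16. The planning statement of 20 subjects and 90% is left unqualified in a document that is written in the past tense and already reports 16.

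A reader can therefore take 90% as the power of the study that was done. If the VAS change were non-significant, that reader would give the result more weight against the planned change than 16 subjects support. The reader cannot correct for this, because the planning mean, standard deviation and any allowance are not given.

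**Working it through.** **Inputs from the Protocol**
- Primary endpoint: VAS pain, before versus after (calculation of the sample).
- Alpha 0.05; 90%, read here as power (assumption).
- Planned n = 20; achieved n = 16 (participants; Intervention).
- Within-group test: paired t (Data analysis). Sidedness is not stated, so both versions are shown.
- Planning mean, standard deviation and pre-post correlation: not given.

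**Shortfall.** 20 − 16 = 4, and 4/20 = 20%.

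**Reproducing the 20.** This cannot be done without the planning mean and standard deviation, so the 20 is neither confirmed nor refuted. Instead, the standardised effect *d* is solved so that 20 subjects give exactly 90% power, and power at 16 is computed with the same *d*.

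**Normal approximation, two-sided**
- d = (z₀.₉₇₅ + z₀.₉₀)/√20 = (1.960 + 1.282)/4.472 = 0.725.
- Power at 16 = Φ(d√16 − 1.960) = Φ(2.899 − 1.960) = Φ(0.939) = 82.6%.

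**Paired t, two-sided (noncentral t)**
- At n = 20: 19 df, critical value 2.093. Power is 90% when d√20 = 3.419, so d = 0.7645.
- At n = 16: 15 df, critical value 2.131, d√16 = 3.058. Power = 81.5%, miss rate 18.5%.

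**All variants with no dropout allowance: power at 16**

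| Method | 90% at n = 20, two-sided | 90% at n = 20, one-sided | 90% at n = 19, two-sided | 90% at n = 19, one-sided |
|---|---|---|---|---|
| Paired t | 81.5% | 82.8% | 83.7% | 84.6% |
| Two-sample t, n per set | 82.1% | 83.1% | 84.1% | 84.9% |
| Normal approximation | 82.6% | 83.5% | 84.5% | 85.1% |

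The n = 19 columns are the limiting case in which 20 was rounded up from just above 19. The range is 81.5% to 85.1%, a miss rate of 14.9% to 18.5% against the planned 10%.

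**If the 20 already held a dropout allowance (two-sided paired t, 90% at the evaluable number)**

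| Allowance | Evaluable target | Power at 16 |
|---|---|---|
| 5% | 20 × 0.95 = 19 | 83.7% |
| 10% | 20 × 0.90 = 18 | 85.8% |
| 15% | 20 × 0.85 = 17 | 87.9% |
| 20% | 20 × 0.80 = 16 | 90.0% |

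**Other readings.** To keep 90% power with 16 (two-sided paired t), the standardised change would have to be 0.868 instead of 0.7645. If 90% is not power and the plan had 80% power at 20, two-sided power at 16 would be 69.5% (paired t) to 70.7% (normal approximation).

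**The case against.** The strongest reply is that nothing is miscalculated. A target of 20 and an achieved 16 can both be true, both are reported openly and near each other, and no sentence says that 90% describes the 16. On this view it is a reporting gap of small consequence: type I error is untouched, the Protocol shows no VAS result that could be misread, and an estimated change with a confidence interval would show the precision without any back-solved effect. The 82% also depends on inputs that cannot be seen. With a 20% allowance, 16 is exactly the evaluable target and nothing is lost. The missing chart may account for the four subjects.

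Much of this is fair and limits the point. It is a reporting matter, and no claim is made that 20 is wrong. The absence of counts should carry no weight while the chart is unavailable. High confidence belongs to the gap between 20 and 16; the size of the loss is conditional. A confidence interval for the VAS change is useful in any case.

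What remains is that the planning statement does not describe the 16 subjects studied, and the text supplies neither an allowance nor a restated power. Counts in a chart would not by themselves supply the power. That both numbers are visible does not let a reader work out which power applies.

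**Conclusion.** The concern holds. The Protocol states a requirement of 20 for the primary endpoint, reports 16, and does not say what power 16 provides. With no dropout allowance, the loss from 90% is 8.5 points under the two-sided paired t (90 − 81.5) and 4.9 points under the most favourable variant (90 − 85.1). An allowance inside the 20 shrinks the loss, to zero at 20%.

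These figures assume that 90% means power and that the planned number gives exactly 90%, or lies at the rounding limit where stated. They hold the planned effect fixed; they are not power computed from the observed result. The effect on interpretation is confined to a non-significant VAS result. It should be fixed, because it concerns the primary endpoint and the correction is very small.

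**What to change.** In the section on calculation of the sample, label the 90% as power and add a statement of what was achieved. For example: 20 were planned for 90% power on the pre-post VAS change; 16 completed, giving about 82% power for the same planned change, conditional on the planning inputs and on no dropout allowance.

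The sponsor should recompute the 82% from the actual planning mean and standard deviation, which it holds, and report those inputs. If the 20 included a dropout allowance, state it and give the matching power instead (two-sided paired t: 85.8% for a 10% allowance, 90% for 20%).

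The cost is one or two sentences, with no extra enrolment and no new analysis. The stated power becomes less favourable unless the 20 already included a 20% allowance.
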